In compliance with the Washington University School of Medicine Institutional Data Safety Monitoring (DSM) Plan, the PI will provide a DSM report to the IRB annually. The PI, research coordinator and members of the research team will review all study data as it becomes available. Investigators not involved with the study will independently review the safety data and state if the study should be continued or not. The report will include the protocol title, IRB protocol number, IND number, the activation date of the study, the number of subjects enrolled to date, the date of first and most recent subject enrollment, a summary of all adverse events regardless of severity or relationship to subject dropouts and corresponding reason for dropout, the investigational plan for the coming year, any new information related to the investigational drug or a summary of any recent literature that may affect the safety and ethics of the study.

12.11 Other Reportable Events:

Major deviations or series of minor deviations having the potential to adversely impact the health, safety, or welfare of participants or others or adversely impact the study's ability to produce scientifically valid results must be reported to the IRB within 10 working days of the occurrence of the event or notification to the Principal Investigator of the event. Major deviations resulting in death of a participant must be reported within one (1) working day of the occurrence of the event or the notification to the Investigator of the event. Any non-

compliance and protocol exceptions or deviations will be documented and maintained in the regulatory binder and participant's research chart.

12.11.1. Non-Compliance and Serious Non-Compliance:

- Noncompliance may occur due to lack of knowledge or due to deliberate choice to ignore regulations, institutional policies, or determinations of the IRB. Noncompliance is defined as failure to follow any applicable regulation or institutional policies that govern human subject's research or failure to follow the determinations of the IRB.
- Serious noncompliance is defined as noncompliance that materially increases risks that results in substantial harm to subjects or others, or that materially compromises the rights or welfare of participants.

12.11.2. Protocol Exceptions and Deviations:

- Protocol exceptions apply only to a single participant or a singular situation. Pre-approval of any protocol exceptions must be obtained by the IRB prior to the event. In the event a situation occurs which requires deviation from the protocol, the PI will make the final judgement on whether or not a participant study is prematurely completed.
- Protocol deviations such as less than expected tracer production can be accounted for during data analysis and will not necessarily result in cancellation of the scan. In the event of any deviations from the investigational plan/protocol that affects the life or physical well-being of a participant in any emergency, the PI will promptly notify the FDA and IRB as required.
- HRPO definitions of minor and major deviations
 - A minor or administrative deviation is one that does not have the potential to negatively impact the rights, safety, or welfare of participants or others or the scientific validity of the study.
 - A major deviation is one that does have the potential to negatively impact the rights, safety, or welfare of participants or others or the scientific validity of the study.

12.11.3. Timeframe for Reporting Required Events

Table 1. Reporting Events

The table below summarizes the timeframe for reporting required events after initial receipt of the information by the PI or member of the research team as described above.

Serious, fatal life-threatening adverse events	IRB	FDA reporting for lemborexant
Any death and immediately life-threatening events, whether related or unrelated and any adverse event that meets the definition of IRB unanticipated	Within one (1) working day to the IRB	As soon as possible but no later than 7 calendar days

Lemborexant 25 mg Overview
[name], Washington University

problem or FDA unexpected and serious suspected adverse reaction.		
Non-fatal/Non-life-threatening adverse events		
Any unexpected and serious suspected adverse reaction, findings from other clinical or animal studies (internal or external) and clinically important increases in severely suspected adverse reactions.	Within 10 working days to the IRB	As soon as possible but no later than 15 calendar days
Annual reportable adverse events		
Adverse events that do not meet the definition of unanticipated problem or serious and unexpected suspected adverse reaction should be submitted cumulatively.	IRB Annual Continuing Review; DSM report	FDA Annual Report
Other reportable adverse events		
New Information that may impact the willingness of subjects to participate in the research study – interim analysis, safety monitoring report, published paper, change in labeling, revised Investigator's Brochure.	Within 10 working days to the IRB	As soon as possible but no later than 15 calendar days
Noncompliance and Protocol Deviations		
A serious noncompliance, major protocol deviation or series of minor deviations which do not meet the above criteria.	Within 10 working days to the IRB	FDA Annual Report.
Non-serious, noncompliance issue	IRB Annual Continuing Review	None unless requested by IRB

13. Privacy/confidentiality

13.1 Breach of privacy/confidentiality:

- All data will be labeled with a random number rather than with any identifiable information. All physical materials (such as paper, data storage disks, and biospecimens) will be stored in locked cabinets/freezers in a locked research area, accessible only to the research team. All electronic information will require a password and will be accessible only to the research team. Any paper or electronic information that could link a participant to the study (such as consent documents) will be stored separately from all other study materials, also in a secure manner that is accessible only to the research team. If a report or article is written about this study or the study data are shared with other researchers, it will be done in such a way that participants cannot be identified.
- For individuals who give verbal consent for the Phone screen, and then do not “pass” the screening questions, their phone screen will be shredded, and *no* information is

kept about them.

Protections for research involving vulnerable populations: This project does not involve vulnerable populations.

13.2 Plan for Adverse Events (AE):

Response to an adverse event or risk will differ based on the type and severity of the event. A Data Safety Monitoring Committee (DSMC) will serve to mitigate these risks and ensure a formal process for dealing with adverse events. A DSMC consisting of experts in the study procedures and the effects of sleep disorders on cardiac and psychiatric morbidities has been established for the proposed study.

- Qualified individuals monitoring the study: The DSMC members have substantial experience and expertise in this area of research and in clinical research, and are qualified to monitor the study.
- The DSMC will meet prior to enrollment of any participants, to review study procedures and potential adverse events, and then provide guidance on HRPO application and consent/informational materials.
- *Web-Based Instruction on Conducting Human Research:* In accordance with the NIH policy effective October 1, 2000, this is to certify that Washington University key personnel involved in the design and conduct of the human subjects research aspect of this proposal have been educated on the protection of human research participants. An interactive web-based program that provides information on conducting human research and the informed consent process is organized into five modules. These modules include detailed information, examples and exercises related to basic principles, history, consent form process, and after approval requirements such as continuing review and adverse events.
- *Review of adverse events:* All personnel who will be in contact with participants and/or data are prepared to identify adverse events and have been instructed to report their occurrence immediately to the principal investigator.
- *Definition:* An adverse event will be defined as any negative change in health related to study-related procedures.
- *Classification of Events:* A Safety Documentation form will assess for details of any adverse events, severity, and relatedness to study procedures.
- *Data Collection Procedures for Adverse Events:* At each visit and with each interaction/phone call, adverse events will be screened for and recorded. If any adverse events have occurred, these will be logged in the Safety Documentation form.
- *Reporting Procedures:* The Safety Documentation form will be discussed during the DSMC meetings. The DSMC will meet according to participant completion goals (e.g., 5 participants complete the study, 10 participants complete the study, 15 participants complete the study, etc.). If a serious adverse event (SAE) occurs, the DSMC will meet as soon as possible to determine the course of action. If the DSMC deems changes to the study are necessary for safety reasons, the study will halt immediately until the changes have been approved through the Washington University HRPO.

- *Safety-related criteria for stopping the study:* The trial will be stopped if there is an unexpected serious adverse event (SAE). Otherwise, circumstances that would warrant stopping the study are not anticipated. However, should any circumstances arise that compromise the safety of the participants, they will be reported to the DSMC who will suspend research until appropriate safeguards allow continuation of the study.
- *Adverse Event Reporting Period:* Serious adverse events and Adverse events, regardless of the causal assessment to the study interventions (lemborexant, lumbar catheter, etc.), are collected from the time the subject signs the study informed consent through 28 days after the participant's last dose of lemborexant. Serious adverse events will be reported directly to Eisai.
 - Expected adverse events (*i.e.*, are listed above and on consent forms) will be discussed at DSMC meetings. Also, they will be reported to the HRPO during annual renewals.
 - Unexpected serious adverse events will be reported within 10 days, per HRPO requirements.

Anticipated adverse events that would require medical intervention are:

- A post-lumbar catheter headache that does not resolve with conservative measures such as rest, hydration, and caffeine intake. This will be treated with “blood patch” in the Clinical Translational Research Unit, at no cost to the participant.
- Side effects to lemborexant such as somnolence and confusion upon waking. Risks from lemborexant are minimized with the inclusion/exclusion criteria and that participants will only receive the drug for 2 nights in the monitored setting of the Clinical Translational Research Unit at Washington University. If any severe adverse events occur after the first dose of lemborexant, then the drug will be discontinued and the participant monitored closely.

14. Potential Benefits of the Proposed Research to Human Subjects and Others

14.1 Potential benefits to participants:

The only direct benefit to the participant is that they will be screened for sleep apnea with the STOP-Bang questionnaire and other sleep disorders by the history and examination of the principal investigator. This may result in a diagnosis that may have otherwise been undetected. Participants who screen fail due to concerns for a sleep disorder like sleep apnea will be informed of the reason for exclusion, withdrawn from the study, and encouraged to follow-up with their primary care physician.

14.2 Potential benefits to others:

Potential benefits to society will be knowledge of whether or not sleep modification can change CSF A β production and concentrations. If CSF A β production and concentrations can be modified by improving sleep efficiency, then this opens up a new potential treatment option for the prevention or treatment of Alzheimer's disease from which they, or future AD patients, may benefit.

Lemborexant 25 mg Overview [name], Washington University

14.3 Risks vs. benefits:

The benefit of the knowledge to be gained in the study, as well as the personal benefit to participants, outweighs the risks in the study. Risks have been minimized to the greatest possible extent, while still achieving the scientific aims of the research study.

15. Importance of the Knowledge to be Gained

The knowledge to be gained in this study is very important because it is the first study directly assessing the relationship of poor sleep efficiency and A β in a relevant human population. If this study is successful, it may lead to treatments targeting sleep for possibly delaying or reducing risk of AD. AD is a devastating neurodegenerative disorder characterized by progressive cognitive decline. The public health impact of dementia is enormous with the number of individuals with AD projected to increase from 5 million Americans in 2010 to 13.5 million Americans in 2050. Even a modest reduction in the risk of AD would have a tremendous public health impact. Demonstrating that sleep alters A β may suggest innovative AD treatment approaches that involve sleep therapies.

16. Data and Safety Monitoring Plan

This study is a clinical trial, however it is not an NIH-defined phase III clinical trial. Lemborexant is FDA-approved for the treatment of insomnia. This study will use lemborexant 25 mg, which is higher than the FDA approved dose. Comparisons are being made between poorly-sleeping older adults treated (lemborexant) and untreated individuals (placebo). There is a Data Safety Monitoring Committee and monitoring plan as described in section “*2.B Protections Against Risk*” above. In compliance with the Washington University School of Medicine Institutional Data Safety Monitoring (DSM) Plan. The PI, research coordinator and members of the research team will review all study data as it becomes available. Investigators not involved with the study will independently review the safety data after 5 participants have completed the study and state if the study should be continued or not. The report will include the protocol title, IRB protocol number, IND number, the activation date of the study, the number of subjects enrolled to date, the date of first and most recent subject enrollment, a summary of all adverse events regardless of severity or relationship to subject dropouts and corresponding reason for dropout, the investigational plan for the coming year, any new information related to the investigational drug or a summary of any recent literature that may affect the safety and ethics of the study.

Given that the study requires significant involvement from the participants, we have taken steps to make the study less taxing for participants. These steps include having nurses available in the CTRU for assisting the research participants at all times and providing 24 hour/7 day/week access to study staff and physicians.

All participants will be identified by a de-identified study number to protect patient confidentiality. Participants may be linked to the “Lemborexant Sleep” study in Epic if they already have a record in the Epic system. Spreadsheets listing the participants’ name and corresponding study number will be managed by the study coordinator, and will be stored in a password protected file behind the Neurology firewall. Only the research team will have

Eisai Inc.

Version 3.0 2023-06-08

CONFIDENTIAL

Page 43 of 58

Lemborexant 25 mg Overview
[name], Washington University

access to this spreadsheet. Data monitoring and analysis will be performed by the principle investigator. Data will also be collected on any adverse events related to the study procedures.

All data from mass spectrometry analyses are electronically uploaded and locked in the [name] laboratory's database (Firebird 2.1.4) blinded to clinical status and other variables. Future studies may involve a collaboration with [name], an A β stable isotope labeling kinetics (SILK) expert in modeling at Washington University, the A β SILK data will be analyzed with the compartmental model using the SAAM II modeling program blinded to clinical status and other variables. All statistical analyses will be conducted in collaboration with [name], an expert in statistics at Washington University, or the ICTS biostatistics core. All data is compared in a pre-specified fashion.

17. ClinicalTrials.gov Requirements

This study will be registered at ClinicalTrials.gov and the final study results will be reported on the website within 12 months of study completion. This will enable registration of primary and secondary aims and allow for broadest publication in journals.

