- Depressed mood and/or suicidal ideations: All participants will be screened for suicidal ideations and psychiatric disorders. All participants with psychiatric disease requiring medications will be excluded both to control this risk and also because psychiatric medications may interfere with sleep. Participants with suicidal ideations will be excluded. This risk is also controlled because participants will only take lemborexant for 2 nights in the monitored setting of the CTRU with 24 hours a day nursing coverage.

10.6 Polysomnogram (PSG):

- Irritation of skin from electrodes used during study: When possible, an alternative cleaning agent or adhesive will be used. If irritation is more than mild, that electrode will not be used for the study.

11. Definitions

For this study, the following standard definitions for reporting will be used:

11.1 Adverse Event:

Adverse Event (AE) is any untoward medical occurrence associated with the use of the study drug in humans, whether or not considered related to the drug. An AE (also referred to as an adverse experience) may include any unfavorable and unintended sign (i.e., abnormal lab test finding), symptom, or disease temporally associated with the use of the drug, and does not imply any judgement about causality.

11.2 Suspected Adverse Reaction:

A suspected adverse reaction is any adverse event that is determined for which there is a reasonable possibility that the study drug caused the adverse event. For IND safety reporting,

Eisai Inc.

Version 3.0 2023-06-08

CONFIDENTIAL

Page 32 of 58

Lemborexant 25 mg Overview

[name], Washington University

'reasonable possibility' means there is evidence to suggest a causal relationship (reasonable possibility) between the drug and the adverse event. A suspected adverse reaction implies a lesser degree of certainty about causality than an adverse reaction.

11.3 Adverse Reaction:

Adverse Reaction means any adverse event caused by a study drug. Adverse reactions are a subset of all suspected adverse reactions where there is a reason to conclude that the drug caused the event.

11.4. Serious:

An adverse event or suspected adverse reaction is considered serious if the event or reaction, in the view of the PI, results in any of the following serious outcomes:

- Death;
- A life-threatening adverse event as defined as placing the participant at immediate risk of death from the AE as it occurred;

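### Section 13.2 collects adverse events of any cause to 28 days after the last dose, but the last scheduled contact falls 3.3-3.5 days after it, and the section's own adverse event definition is narrower than its collection rule

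*Combined protocol and SAP*

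**What the plan says.** The Reporting Period bullet of 13.2 states that adverse events and serious adverse events "are collected from the time the subject signs the study informed consent through 28 days after" the last dose, "regardless of the causal assessment to the study interventions (lemborexant, lumbar catheter, etc". The mechanism is in the Data Collection bullet: "At each visit and with each interaction/phone call, adverse events will be screened for and recorded".

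After discharge, 7.4.4 and the schedule in Appendix 2 provide two phone calls, at 24 and 48 hours. Neither place lists a later visit or call. Section 7.4.4 asks participants to contact the team about physical complaints, and 10.3 gives them a round-the-clock number.

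On what counts as an adverse event, the Definition bullet of 13.2 reads: "An adverse event will be defined as any negative change in health related to study-related procedures". The Classification bullet says: "A Safety Documentation form will assess for details of any adverse events, severity, and relatedness to study procedures". Section 11.1 defines an adverse event as "any untoward medical occurrence associated with the use of the study drug in humans, whether or not considered related to the drug". Section 11.11 documents all events whatever their suspected cause, and 7.4 records all adverse events at each visit.

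**The concern.** Two separate things do not fit together.

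First, the collection window is much longer than the schedule of contacts that would fill it. A late event that the participant does not volunteer may go unrecorded, although 13.2 presents it as collected. The passive route is also narrower than the window: 7.4.4 words it for physical complaints, whereas 10.5 includes depressed mood and suicidal ideation among the potential events. Safety rules such as the prompt DSMC meeting after a serious adverse event can act only on events that someone has learned of.

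Second, staff who follow the Definition bullet as written would leave out unrelated events that the same section says are collected. The form that carries events to the DSMC ("The Safety Documentation form will be discussed during the DSMC meetings") is described as judging relatedness to procedures only, in a trial whose intervention is a drug.

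**Working it through.** **Part 1: timing of the last scheduled contact.**

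The 28 days is a stated rule, so there is no plan figure to reproduce. Inputs:
- Last dose: hour 25 (7.4.4).
- Catheter removal and end of sampling: hour 48 (3.1).
- Observation before discharge: 8-12 hours (7.4.4).
- Last call: 48 hours after discharge (7.4.4, Appendix 2).
- Window: 28 × 24 = 672 hours after the last dose (13.2).

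Steps:
- Discharge: 48 + 8 = hour 56, to 48 + 12 = hour 60.
- Last call: 56 + 48 = hour 104, to 60 + 48 = hour 108.
- Time since last dose: 104 − 25 = 79 h (3.29 days), to 108 − 25 = 83 h (3.46 days).
- Window left without scheduled contact: 672 − 83 = 589 h (24.5 days, 87.6%), to 672 − 79 = 593 h (24.7 days, 88.2%).

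Variants:
- Approximate clock times in 3.1 (dose about 22:00 on Day 2, end about 20:00 on Day 3, so 22 hours apart): 22 + 8 + 48 = 78 h, to 22 + 12 + 48 = 82 h (3.25-3.42 days).
- Only the first dose taken (hour 1), with the same discharge time: 103-107 h (4.29-4.46 days).
- Section 3.1 gives the observation as at least 8 hours, so a stay beyond 12 hours is possible. No plausible extension brings the call near day 28.

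**Part 2: the definitions side by side.**

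- 13.2 Definition: the change must be related to study procedures.
- 13.2 Reporting Period: any causality, from consent onward.
- 11.11 and 7.4: all adverse events are documented or recorded.
- 13.2 anticipated events: these include "Side effects to lemborexant such as somnolence and confusion upon waking".
- 11.1: whether or not related to the drug, but tied to use of the study drug.

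Take the Definition bullet on its most generous reading, with dosing counted as a study procedure. Lemborexant side effects then qualify, but an unrelated event still does not, so the conflict with the Reporting Period bullet, 11.11 and 7.4 remains. On a narrow reading, with dosing not a procedure, the bullet also conflicts with the side effects that 13.2 itself anticipates. Section 11.1 does not settle the matter, because it does not clearly cover events between consent and the first dose, which the Reporting Period includes.

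The Classification bullet names relatedness to procedures only. Section 11.8 asks about the study drug or a visit procedure, and the five grades in 11.10 refer to drug or procedure. The description of the form is therefore narrower than the assessment the protocol requires.

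**The case against.** The strongest reply on Part 1 is that a reporting period is not a promise of active contact throughout it. Participants are told to call and have a number to use, and dosing is two nights in a monitored unit. It stands to this extent: a collection route exists, and late drug-related events may be few. But 13.2 says that events are collected and describes screening at contacts as the means, and no contact falls in the last 24.5 days. The follow-up to resolution in 11.11 applies to reportable events already known; it does not find new ones.

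On Part 2, the reply is that the rest of the safety system covers the gap, and much of this stands. A reader might infer the following, none of which the documents support:
- **That drug attribution has nowhere to be recorded.** Section 11.12 provides an AE form for the investigator's determination and an AE log, and 11.8 requires an assessment report with any reportable event. The Safety Documentation form itself is not in the documents, so only its description can be criticised.
- **That drug reactions never reach the DSMC.** Section 13.2 takes expected adverse events to DSMC meetings, and the monitoring report in sections 12.10 and 16 summarises all adverse events.
- **That notice to the manufacturer would fail.** The Reporting Period bullet sends serious adverse events to the manufacturer without a relatedness filter.
- **That all of 13.2 opposes the Definition bullet.** The Classification bullet shares its narrow wording; the conflict is with the Reporting Period and anticipated-event text.
- **That the catheter headache rate in 9.1 measures the problem.** Those headaches meet the narrow definition and would be captured, and placebo participants have no drug exposure to attribute them to.

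**Conclusion.** Both parts hold, at modest severity. About 88% of the stated 28-day window has no scheduled contact, and the 13.2 definition excludes unrelated events that 13.2, 7.4 and 11.11 say are collected or recorded.

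The timing rests on the nominal hours in 3.1 and 7.4.4 and does not depend on which variant is used. The 88% must not be read as a share of events missed: the documents give no late-event rate, and participant reports may capture some or all of them. Nor do the documents support a claim of bias between arms, since the schedule is the same for both, or of an effect on a planned analysis.

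**What to change.** 1. Add one scripted adverse-event phone screen at the end of the protocol's own 28-day window to 7.4.4 and Appendix 2, using the screen 13.2 already applies at each call. Cost: at most 30 short calls by existing staff, one per participant, plus the logging of some unrelated minor events. A sentence saying that late collection is participant-reported would make the text accurate, but on its own would not make the window ascertainable.

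2. Use one definition in both 11.1 and 13.2: any untoward medical occurrence from signed consent to the end of the window, whether or not related to study drug or study procedures. Changing 13.2 alone would leave 11.1 tied to drug use. Cost: two text edits.

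3. Have the Safety Documentation form record relatedness to drug and relatedness to procedure as separate items, each with the 11.10 grades. Cost: one added form field and a matching Classification bullet.

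Editorial only: the sentence in section 16 about collecting procedure-related adverse events can be aligned at the same time, and the window can be worded as running from the last dose of study drug so that it plainly covers placebo participants.
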